Official Study Title

Improving Prenatal Care to Reduce Early Onset Preeclampsia in Low-Income Black Women in Kansas

ClinicalTrials.gov Identifier

NCT Number: *Pending registration at ClinicalTrials.gov*

Principal Investigator

[name], PhD

University of Kansas Medical Center (KUMC)

Study Sponsor

National Institutes of Health (NIH)

IRB Protocol Number

STUDY00160319

Version Date of This Protocol Document

February 9, 2026

Site Name: University of Kansas Medical Center

Kansas City, Kansas

University of Kansas Medical Center
RESEARCH PROTOCOL INVOLVING HUMAN SUBJECTS
TEMPLATE WITH GUIDANCE

Version date: 02.09.2026

Principal Investigator: [name]

Study Title: *Improving Prenatal Care to Reduce Early Onset Preeclampsia in Low-Income Black Women in Kansas*

[name], [name], [name], [name], [name]

1. Protocol Synopsis

Study Design

Prospective, two-arm randomized controlled trial; parallel assignment; open-label (behavioral/telehealth intervention).

Randomization: 2:1 allocation using REDCap with variable block sizes.

Framework: Practical, Robust Implementation, and Sustainability Model (PRISM) to guide implementation, adoption, effectiveness, maintenance, and pragmatism evaluation.

Population

Pregnant participants, age ≥ 18 years.

English or Spanish speaking.

Less than 13 weeks gestation at enrollment.

Moderate or high risk for preeclampsia per USPSTF criteria.

Intervention (Arm 2)

Centering HER (HGPC-T): routine prenatal care plus 7 doula-led virtual group sessions (90 minutes each) with OB/GYN fellow oversight.

Participants receive Bluetooth BP cuff and (if applicable) Apple Watch; self-monitor and self-report blood pressure and weight; complete surveys and medication log (if applicable).

Comparator (Arm 1)

Usual doula prenatal care and routine prenatal care visits with OB/GYN; completes study surveys.

Primary/Key Outcomes (as stated in source protocol)

Blood pressure rates; hypertension monitoring and aspirin compliance (# of women monitoring BP and aspirin compliance).

Feasibility, acceptability, and contextual factors required for implementation.

Duration

Enrollment at <13 weeks gestation through postpartum survey completion (baseline, antepartum, and postpartum surveys).

Data Sources

REDCap surveys (baseline, antepartum, postpartum).

Self-reported BP/weight (device-supported); medication log (if applicable).

Electronic health record abstraction (clinical outcomes) as described in the source protocol.

I. Purpose, Background and Rationale

A. Aim and Hypotheses

1. The study will use the Practical, Robust Implementation, and Sustainability Model (PRISM) to implement **Hypertension group prenatal care**- telehealth (HGPC-T) also known as Centering HER-health, empowerment, reproduction to reduce preeclampsia in pregnancy (centering GPC, screening, monitoring, and aspirin) in community clinics.¹⁸

Based on PRISM, we will assess HGPC-T intervention development (e.g., organizational, providers, and patients' perceptions); adoption (e.g. HGPC-T intervention adoption); the effectiveness (e.g., # of women monitoring hypertension and aspirin compliance); maintenance (e.g. intention to continue the HGPC-T); and pragmatism (e.g., adaptability of HGPC-T in other settings).¹⁸ The central hypothesis is that HGPC-T will lead to continuous monitoring of chronic hypertension, reduce early-onset preeclampsia, and reduce barriers to prenatal care.

2. Aim 1. To determine the feasibility, acceptability, and contextual factors required for the implementation of the virtual GPC-T to reduce preeclampsia among low-income, predominantly Black women. Aim 2. To pilot the virtual GPC-T and determine whether virtual HGPC-T reduces preeclampsia among low-income, predominantly Black women. Aim 3. To determine the effectiveness of virtual GPC to reduce preeclampsia among low-income, predominantly Black women.

B. Background and Significance

1. Study Significance: This research has the potential to reduce preeclampsia disparities by considering system change in the delivery of maternal care, continuous monitoring of blood pressure, reducing barriers in transportation and time off from work, improving patient hypertension education, and improving social support and peer-to-peer learning.
2. First, the study will allow us to determine the feasibility, acceptability, and contextual factors required for the implementation of the HGPC-T to reduce disparities in EOP, which to our knowledge, has not yet been done. Second, diverging from the status quo of individual prenatal care treatment to reduce EOP, implementation of 81 mg of aspirin⁶ between 16 and 20 weeks, this study will pilot the virtual HGPC-T enhancement with a hypertension intervention known to improve medication adherence and decrease hypertension to reduce preeclampsia.
3. Literature Review: (see Reference List)
4. **Importance of preeclampsia in the U.S.** Preeclampsia, a potentially fatal pregnancy condition characterized by high blood pressure, is estimated to complicate 3 percent to 6 percent of all pregnancies¹⁻². The rate of preeclampsia in the U.S. has increased 25 percent in the past two decades²². Preeclampsia is a leading cause of maternal and infant illness and death^{1;4-5;8}. Non-Hispanic Black women carry a 3- to 4 fold greater risk of dying from pregnancy-related preeclampsia^{3;12;20}. For example, preeclampsia is associated with 20-30% preterm births and 15% low birth weight^{1;5}. Moreover, a significant number of women who get preeclampsia are at increased risk for cardiovascular disease after pregnancy and throughout their lives.^{1;8;23}

C. Rationale

1. We posit that the implementation of HGPC-T for continuous high blood pressure monitoring is a critical step in closing disparities in preeclampsia. This research has the potential to reduce preeclampsia disparities by considering system change in the delivery of maternal care, continuous monitoring of blood pressure, reducing barriers in transportation and time off from work, improving patient hypertension education, and improving social support and peer-to-peer learning.
2. This research has the potential to reduce preeclampsia disparities by considering system change in the delivery of maternal care continuous monitoring of blood pressure, reducing barriers in transportation and time off from work, improving patient hypertension education, and improving social support and peer-to-peer learning.

3. The study may reduce preeclampsia and improve management of pregnancy-related hypertension.

II. Research Plan and Design

- A. Study Objectives:** The objective is to enhance the Centering GPC intervention with telehealth and take care of your blood pressure (TCYB) intervention for hypertension monitoring.
- B. Study Type and Design:** We will use REDCap software to assign 72 women in a 2:1 randomization scheme in variable block sizes to, respectively, Centering -Health, Empowerment, Reproduction (HER) or usual doula care. You will have a 2 out of 3 chance to participate in the intervention. "Group assignments are random, like flipping a coin or rolling the dice."
- i. Group 1-Non-Intervention
 1. Receive usual doula prenatal care including regular prenatal care visits.
 2. Participants will complete a baseline survey, antepartum study survey, and for postpartum survey
 - ii. Group 2- Centering HER intervention
 1. Once selected for the study, you will participate in usual prenatal care visits with an OBGYN, 7 doula led virtual intervention sessions visits with an OBGYN fellow oversight.
 2. The 7 virtual meeting will be an hour and a half and led by a doula. A research staff member will be present to help with the coordination of the virtual intervention.
 3. You will receive 7 virtual visits with a group of women participating in the study
 4. Each telehealth/virtual visit will discuss blood pressure/hypertension, blood pressure, nutrition, weight management, exercise, and risk factors for hypertension.
 5. Participants will receive a Bluetooth blood pressure cuff, apple watch (if applicable), and doula tailored care to take your blood pressure and weight at home.
 6. Self-report blood pressure and weight
 7. Participants will complete a baseline survey, antepartum study survey, and for postpartum survey.
 8. Keep a medication log if applicable

Intervention Table

Feature	Group 1: Non-Intervention (Usual Doula Care)	Group 2: Centering HER Intervention
Prenatal Care	Standard doula support + routine prenatal care with OB/GYN	Routine prenatal care + 7 virtual doula-led intervention sessions with OB/GYN fellow oversight

Feature	Group 1: Non-Intervention (Usual Doula Care)	Group 2: Centering HER Intervention
Doula Involvement	Yes – access to traditional doula support during prenatal visits	Yes – virtual group doula-led health education and coaching
Group Sessions	None	7 virtual group sessions (90 min each) with other pregnant participants
Session Topics	Not applicable	Hypertension, blood pressure, nutrition, exercise, risk factors
Technology Provided	None	Bluetooth BP cuff, Apple Watch (if applicable)
Self-Monitoring	No	Participants self-monitor and report blood pressure and weight
Survey Completion	Baseline, antepartum, and postpartum surveys	Baseline, antepartum, and postpartum surveys
Medication Tracking	No	Keep medication log (if applicable)
Research Staff Involvement	Minimal such as surveys, reported blood pressure	Yes – staff assist with coordinating virtual sessions

Timeline

Month	Activities	Milestones / Notes
Month 0-December	Study Launch + IRB Finalization– Finalize recruitment materials– Train staff + doulas– Set up data tracking and virtual platforms	IRB approval confirmed; staff orientation completed
Month 1-February	Recruitment Begins– Begin enrolling both groups (target ~5 per group)– Distribute flyers, contact clinics, etc.	First 10 participants enrolled (5 intervention, 5 control)
Month 2-3	Continue Recruitment + Begin Intervention– Enroll next 10 participants– Begin Group 1 surveys– Intervention Group 1 starts Session 1	~50% enrollment milestone reached
Month 4	Recruit Final Cohort– Enroll remaining 36 participants– Distribute Apple Watches and BP cuffs– Start Sessions 1–2 for final intervention groups	72 participants fully enrolled (36 per group)
Month 5	Midpoint Engagement– Intervention: Sessions 3–4 (Blood Pressure, Nutrition)– Track self-monitoring data– Group 1 completes mid-surveys	Monitor adherence and troubleshoot any tech issues
Month 6	Continue Sessions + Surveys– Sessions 5–6: Physical activity, medication awareness– Group 2 logs vitals– Group 1 continues routine care + surveys	Most intervention participants complete 75% of sessions
Month 7	Final Session + Postpartum Planning– Session 7: Doula support, preparing for delivery– Collect	Sessions concluded for intervention group

Month	Activities	Milestones / Notes
	antepartum surveys– Encourage postpartum follow-up prep	
Month 8	Final Data Collection + Postpartum Surveys– Collect postpartum survey from both groups– Finalize weight/BP logs– Export and clean dataset	Study concludes; prepare for analysis and reporting

C. Sample size, statistical methods, and power calculation

1. Data will be checked for errors, inconsistencies, and missing values. Descriptive statistics (e.g., mean and standard deviation for continuous variables and number and percent for categorical variables) will be presented for all demographic variables, predictors of interest, and outcomes. Chi-square and 2-sample t-tests will be used to compare the outcomes among demographic groups and between different treatments.
2. The participants will receive education on nutrition and exercise, will be asked to monitor their blood pressure daily using blood pressure cuffs, and will receive the standard of care of 81mg of aspirin per day (if applicable).
3. This is a pilot project, so there is no power calculation for the project. The total number of participants is 72.

D. Subject Criteria (See Vulnerable Populations appendix, if applicable):

1. Inclusion criteria: English or Spanish speaking, <13 weeks gestations, >18 years old, moderate or high risk for preeclampsia according to the United States Preventative Services Task Force (USPSTF): **High Risk:** History of preeclampsia (especially with an adverse outcome); Multifetal gestation; Chronic hypertension; Pregestational type 1 or type 2 diabetes; Kidney disease; Autoimmune disease (e.g., systemic lupus erythematosus, antiphospholipid syndrome) **Moderate Risk:** Nulliparity (first pregnancy); Obesity (pre-pregnancy BMI > 30); Family history of preeclampsia (mother or sister); Black persons (due to social, not biological, factors); Lower income; Age ≥ 35 years; Personal history factors (e.g., low birth weight or small for gestational age, previous adverse pregnancy outcome, >10-year pregnancy interval); In vitro conception (IVF)
2. Exclusion criteria: <18 and not receiving prenatal care or eligible for doula care
3. Withdrawal/Termination criteria: N/A

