4. N/A

E. Specific methods and techniques used throughout the study

1. Laboratory tests: **N/A**
2. **Study Procedures:** The control group will receive usual care from OBGYN and usual doula counselling and complete surveys. The study's intervention will be conducted as 7 usual care visits with OBGYN and 7 virtual group visits, including a group of women in the study. Each participant will also have access to usual doula counselling. Each virtual visit will discuss nutrition, high blood pressure/hypertension, exercise, weight

management, and risk factors for hypertension. Each participant will receive a blood pressure cuff and scale to take their blood pressure and weight at home.

3. Each participant will be expected to complete a consent, attend virtual group sessions, complete the medication log if applicable and complete the surveys.

4. **N/A**

5. Timeline: **N/A**

F. Risk/benefit assessment:

1. Foreseeable Risks

- Privacy and confidentiality: risk of unintended disclosure of pregnancy/health information through study records or virtual sessions.
- Group-session confidentiality limits: other participants may share information outside the group despite agreements.
- Psychological or emotional discomfort: discussing pregnancy, health behaviors, barriers to care, or social stressors may be upsetting.
- Device-related risks: minor discomfort with cuff use; anxiety related to elevated readings; potential for inaccurate readings.
- Time and inconvenience: time required for surveys, virtual sessions, and daily BP/weight monitoring.

2. Risk Mitigation

- Use REDCap and secure institutional storage (p:protecteddata drive) with role-based access; store identifiers separately from analytic datasets.
- Use virtual-session ground rules and confidentiality agreements; allow participants to use first name or preferred name in group.
- Provide clear instructions that participants should not change medications based on home readings without contacting their clinician; provide escalation guidance for severe readings.
- Offer option to skip any survey question and request private follow-up for sensitive concerns

3. Potential Benefits

- Consistent with the source protocol, potential benefits include improved ability to monitor blood pressure, increased hypertension education, and peer-to-peer social support; benefits are not guaranteed.

G. Location where study will be performed: University of Kansas Medical Center

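### BP monitoring and aspirin compliance are a key effectiveness outcome, but the arm definitions give the cuff, self-monitoring and medication log to Arm 2 only, and other sections disagree on who monitors

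*Protocol*

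**What the plan says.** **The outcome.** The Synopsis lists "hypertension monitoring and aspirin compliance (# of women monitoring BP and aspirin compliance" under Primary/Key Outcomes. Section I.A gives the same measure as its example of "the effectiveness (e.g., # of women monitoring hypertension and aspirin compliance" and names adoption as a separate PRISM element. Sections II.C.1 and V.A plan chi-square and two-sample t-tests of outcomes between treatments.

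**The arms.** In the Intervention Table (II.B), Group 1 has None for technology and No for both self-monitoring and medication tracking. The rows read "Self-Monitoring No Participants self-monitor and report blood pressure and weight" and "Medication Tracking No Keep medication log (if applicable", with Group 1 first and Group 2 second. The Synopsis agrees: cuff, self-reporting and medication log appear under Arm 2, and surveys are the only study data task listed for Arm 1.

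**Text that points elsewhere or names no arm.**
- The same table describes research staff contact for Group 1 as "Minimal such as surveys, reported blood pressure".
- II.C.2 has the participants monitoring BP daily with cuffs and names no arm.
- II.E.2, after describing both arms, says "Each participant will receive a blood pressure cuff and scale to take their blood pressure and weight at home".
- II.E.3 expects each participant to attend the virtual groups, "complete the medication log if applicable and complete the surveys".
- IV.E.1 lists self-reported BP and medication adherence as data sources, with no arm named.

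**The concern.** Taking one's blood pressure at home with a supplied cuff, and recording tablets in a supplied log, are parts of the intervention. A comparison with an arm that was given neither shows that they were handed out. It does not show that group care changed behaviour or reduced hypertension. A small p-value on this measure could be published as evidence of effectiveness and used to justify a larger trial.

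The two halves of the outcome fail in different ways. Self-monitoring risks a large difference that carries little information. Aspirin compliance risks having no control data to compare with. The conflicting arm descriptions add a third difficulty: as written, a site could not tell from the protocol whether a control woman should receive a cuff or report readings.

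**Working it through.** The protocol gives no power, effect size or alpha for this outcome, so there is no figure to reproduce. Two-sided 0.05 is assumed below.

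**Inputs.** Total 72, allocated 2:1 (II.B): 72 × 2/3 = 48 in Arm 2 and 72 × 1/3 = 24 in Arm 1. The timeline in II.B instead states 36 per group, which is used as a sensitivity case. Controls scored 0 on self-monitoring is an assumption; no section states it.

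**Step 1: smallest Arm 2 count giving p < 0.05 against 0 controls.** With k of n1 in Arm 2, 0 of n0 in Arm 1 and N = n1 + n0, the uncorrected Pearson statistic reduces to

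X² = N·k·n0 / [(N − k)·n1].

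- k = 6: 72·6·24 / (66·48) = 3.27, p = 0.070
- k = 7: 72·7·24 / (65·48) = 3.88, p = 0.049
- k = 24: 72·24·24 / (48·48) = 18.0, p = 0.00002

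At k = 7 the expected control count is 24·7/72 = 2.3, too small to rely on the uncorrected test, so all three common tests are shown:

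| Test | 48 vs 24 | 36 vs 36 |
|---|---|---|
| Pearson | 7/48 (14.6%), p = 0.049 | 4/36 (11.1%), p = 0.040 |
| Fisher | 8/48 (16.7%), p = 0.046 | 6/36 (16.7%), p = 0.025 |
| Yates | 10/48 (20.8%), p = 0.041 | 6/36 (16.7%), p = 0.033 |

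**Step 2: how often this happens when behaviour is really equal.** Suppose the same true proportion monitors in both arms (48 vs 24). The rejection probability, by exact enumeration, is:

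| True proportion, both arms | Same item in both arms: Pearson / Fisher | Controls scored No: Pearson / Fisher |
|---|---|---|
| 20% | 5.3% / 3.3% | 87% / 77% |
| 30% | 5.4% / 3.5% | 99.6% / 98.9% |
| 50% | 5.5% / 3.9% | about 100% / about 100% |
| 70% | 5.4% / 3.5% | about 100% / about 100% |

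Significance still needs some uptake. At 10% true uptake in Arm 2 with controls at zero, the probability of p < 0.05 is 20% (Pearson) or 10% (Fisher).

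**Step 3: aspirin.** This calculation does not carry over. No medication tracking in Group 1 means that compliance is unrecorded, not that it is zero; II.C.2 describes aspirin as standard of care where applicable, so control women may take it. In the Appendix E inventory, the only instrument whose stated purpose is aspirin adherence is the medication log, which the table gives to Arm 2. EHR abstraction there covers blood pressure, care utilization and delivery outcomes.

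**Step 4: the measure as a one-arm description.** For illustration only, if 36 of 48 Arm 2 women monitored, the proportion is 75% with a Wilson 95% interval of 61% to 85%. That is useful information about uptake in a pilot.

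**The case against.** The strongest reply is that the protocol never says controls will be scored as non-monitors and never singles this outcome out for a between-arm test. The testing sentence is generic, and I.A offers the measure as an example within PRISM. Both arms complete three surveys, and Appendix E describes the antepartum survey as holding outcomes and process measures. Its content is not shown, so a common item may exist. The study is also an unpowered pilot, and blood pressure rates, the only outcome named in V.B, can come from EHR abstraction in both arms.

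Much of this stands, and it rules out four stronger readings that a reader might infer:
- *That the outcome is collected only in Arm 2.* This is true of the Synopsis and the Intervention Table, but II.B's staff row, II.E and IV.E can be read as including Group 1, and the survey content is unknown.
- *That the result is significant by construction.* It needs zero scoring of controls and Arm 2 uptake of roughly 15% to 21%. Under that scoring significance is very likely at any reasonable uptake, but it is not automatic.
- *That aspirin compliance will differ significantly.* Unrecorded is not zero.
- *That controls receive the active component and dilute the contrast.* In II.E.2 the sentence on the cuff and scale follows the description of the intervention, and II.E.3 has each participant attending groups that the table denies to Group 1. Loose drafting about Arm 2 is the likelier explanation.

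What does not fall away: a measure named as key and as effectiveness is the intervention's own activity, the named instruments for it belong to one arm, and the sections disagree. These are matters of arm definition and data collection. A later analysis plan cannot recover adherence that was never asked of controls.

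**Conclusion.** The point holds in a limited form. Under the arm definitions in the Synopsis and the Intervention Table, a between-arm comparison of BP self-monitoring mainly reflects delivery of the intervention. If controls are scored No, p < 0.05 is reached at 7 to 10 of 48 women (15% to 21%), or at 4 to 6 of 36 under the timeline's equal groups. Those figures rest on the assumed scoring and an assumed two-sided 0.05 level.

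For aspirin compliance the defect is a comparator with no named instrument, which prevents a valid comparison but does not predetermine one. The conflict over who has a cuff, reports BP and keeps a log stands on the text alone and needs no calculation. The conclusion does not extend to blood pressure rates.

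**What to change.** 1. Report BP self-monitoring and log completion as Arm 2 adoption or fidelity, each as a proportion with a 95% confidence interval, and do not test them against Arm 1. This costs a change of label and gives up a comparison that would have said little.
2. If aspirin compliance is to be compared between arms, take it from one identical item in the antepartum survey, which both arms already complete. Restrict the comparison to women for whom aspirin is recorded as applicable by the same rule in both arms, and keep the Arm 2 log descriptive. A baseline item would not serve: baseline is before 13 weeks, whereas I.B.2 refers to aspirin between 16 and 20 weeks. A fixed gestational-age window would not match an antepartum survey tied to the last visit before delivery (III.G, Appendix E). The cost is one survey item and a common applicability record; the drawback is self-report recalled late in pregnancy.
3. Reconcile the Intervention Table, II.C.2, II.E.2, II.E.3 and IV.E.1 into one statement of which arm receives the cuff and scale, which reports BP and which keeps the log. Which arrangement is intended is for the investigators to say. This is an editing change, best made before control data are collected.

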2. N/A

V. Data Analysis and Reporting

- A. Statistical and Data Analysis:** Data will be checked for errors, inconsistencies, and missing values. Descriptive statistics (e.g., mean and standard deviation for continuous variables and number and percent for categorical variables) will be presented for all demographic variables, predictors of interest, and outcomes. Chi-square and 2-sample t-tests will be used to compare the outcomes among demographic groups and between different treatments.
- B. Outcome:** Blood pressure rates
- i. Hypertensive-range BP is defined as SBP ≥ 140 and/or DBP ≥ 90 mm Hg; severe-range BP is SBP ≥ 160 and/or DBP ≥ 110 mm Hg.
 - ii. Severe-range hypertension (obstetric emergency threshold): SBP ≥ 160 or DBP ≥ 110
- C. Study results to participants:** N/A
- D. Publication Plan:** Three publications will be done: Implementation of the study, analysis of study results, and health behaviors of participants.
- E. Bibliography / References / Literature Cited**

2. ACOG. Gestational Hypertension and Preeclampsia. *Obstetrics & Gynecology* 2019;133:1-25.
4. Sibai B. Diagnosis and Management of Gestational Hypertension and Preeclampsia. *Obstetrics and Gynecology (New York 1953)* 2003;102:181-192.
5. Backes CH. Maternal preeclampsia and neonatal outcomes. *Journal of pregnancy* 2011;2011:1-7.
8. Raymond D. A critical review of early-onset and late-onset preeclampsia. *Obstetrical & gynecological survey* 2011;66:497-506.

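### Aims 2 and 3 promise to determine an effect on preeclampsia, but preeclampsia is not a listed or defined outcome and 72 women cannot support an effectiveness conclusion

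*Protocol*

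**What the plan says.** **Aims and hypothesis (Protocol I.A).** Aim 2 is "To pilot the virtual GPC-T and determine whether virtual HGPC-T reduces preeclampsia among low-income, predominantly Black women". Aim 3 is "To determine the effectiveness of virtual GPC to reduce preeclampsia among low-income, predominantly Black women". The central hypothesis is that the programme will, among other things, "reduce early-onset preeclampsia, and reduce barriers to prenatal care".

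**Outcomes.** The first item under the synopsis heading for primary and key outcomes is "Blood pressure rates; hypertension monitoring and aspirin compliance (# of women monitoring BP and aspirin compliance"; the second is feasibility, acceptability and context. Section V.B gives the outcome as "Blood pressure rates", followed by the 140/90 and 160/110 mm Hg thresholds. The EHR paragraph in IV.D mentions delivery outcomes and diagnoses bearing on preeclampsia risk. The EHR row of Appendix E mentions blood pressure, care utilisation and delivery outcomes. Neither names preeclampsia as an outcome.

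**Size and test.** Section II.C fixes 72 participants and states: "This is a pilot project, so there is no power calculation for the project". Sections II.C and V.A both state: "Chi-square and 2-sample t-tests will be used to compare the outcomes among demographic groups and between different treatments".

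**Allocation.** The synopsis and II.B give 2:1, which is 48 and 24. The timeline table in II.B shows 36 women in each group at full enrolment.

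**Event rate.** The only incidence figure is in I.B, where preeclampsia "is estimated to complicate 3 percent to 6 percent of all pregnancies". Entry is restricted to women at moderate or high risk (II.D), for whom no rate is given.

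**The concern.** Two of the three aims pose a confirmatory question about a clinical diagnosis, while the outcome section measures something else. Followed as written, the trial would collect blood pressure data and have no declared endpoint for Aims 2 and 3. A woman who entered with chronic hypertension can reach 140/90 without preeclampsia, so the defined thresholds do not answer those aims.

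A pilot needs no power calculation, but it then cannot also undertake to determine effectiveness. Under the present wording a null comparison could be read as evidence that the programme does not work, and a chance imbalance in a handful of cases as evidence that it does.

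**Working it through.** The plan gives no power or sample-size derivation to reproduce, so the check asks what 72 women could show.

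**Inputs from the Protocol:** N = 72 (II.C); 2:1 allocation, so 72 × 2/3 = 48 and 72 × 1/3 = 24 (II.B); 3-6% incidence in all pregnancies (I.B); chi-square test (II.C, V.A).

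**Assumptions, not in the Protocol:** two-sided level 0.05; a true halving of risk; no dropout; control risks of 10%, 15% and 25% to cover a raised-risk population.

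**Step 1: expected cases if both arms share the risk p.** Total = 72p; control arm = 24p. For example, 72 × 0.03 = 2.16 and 72 × 0.06 = 4.32.

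**Step 2: exact power for a halving.** Sum Bin(x; 48, p/2) × Bin(y; 24, p) over all pairs of case counts (x, y) for which the test gives p < 0.05 in favour of the intervention.

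**Step 3: total N for 80% power at 2:1.** With p1 = control risk, p2 = p1/2 and pooled risk P = (p1 + 2p2)/3, the control-arm size is

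[1.96 √(1.5 P(1−P)) + 0.8416 √(p1(1−p1) + p2(1−p2)/2)]² / (p1−p2)².

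At 3%, P = 0.02 and the result is (0.3361 + 0.1608)² / 0.000225 ≈ 1,097.1. This rounds up to 1,098 controls, or 3 × 1,098 = 3,294 women.

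| Control risk | Expected cases in 72 | Expected in 24 controls | Power, Pearson | Power, Fisher | Total N for 80% |
|---|---|---|---|---|---|
| 3% (all pregnancies) | 2.16 | 0.72 | 8% | 2% | 3,294 |
| 6% (all pregnancies) | 4.32 | 1.44 | 12% | 6% | 1,611 |
| 10% (assumed) | 7.2 | 2.4 | 14% | 11% | 936 |
| 15% (assumed) | 10.8 | 3.6 | 17% | 14% | 600 |
| 25% (assumed) | 18.0 | 6.0 | 28% | 21% | 330 |

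With 36:36 arms, power at 25% is 27% (Pearson) or 19% (Fisher), so the allocation conflict does not change the conclusion. Early-onset disease is a subset of all preeclampsia and would yield fewer cases.

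**Step 4: precision at the most favourable rate.** At 25% in both arms, the approximate 95% half-width for the risk difference is 1.96 × √(0.25 × 0.75 × (1/48 + 1/24)) = 1.96 × 0.108 = 0.21, or 21 percentage points. A halving is 12.5 points.

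**Step 5: the named test on sparse counts, if it were applied to preeclampsia.** Take 0/48 against 2/24. Uncorrected Pearson is 72 × (48 × 2)² / (48 × 24 × 2 × 70) = 663,552 / 161,280 = 4.11, p = 0.043. The smallest expected count is 24 × 2/72 = 0.67. The Yates-corrected p is 0.205. Fisher gives C(24,2)/C(72,2) = 276/2,556 = 0.108. The form of the test therefore decides the reading.

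**The case against.** The Protocol openly calls itself an unpowered pilot, Aim 2 begins with piloting, and I.A describes effectiveness within the implementation framework as monitoring and aspirin compliance. On that view the aims are only loosely worded. That softens the intent but not the text: Aim 3 names preeclampsia, and the outcome that answers an aim belongs in the protocol, not only in an analysis plan.

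Four stronger readings are tempting and are not supported:

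- **That the trial should expect about 2 to 4 cases.** This applies a rate for all pregnancies to women selected for raised risk. At an assumed 10-25% the figure is 7 to 18. The low figure needs that label.
- **That two cases would be declared a significant benefit.** This requires both cases in the control arm, 48:24 arms, a two-sided 0.05 level and no continuity correction. The Protocol states neither the level nor the form of chi-square. With 36:36 arms the same split gives an uncorrected p of 0.15.
- **That the test generally errs towards the intervention.** With no true effect and 48:24 arms, uncorrected Pearson falsely shows benefit in 3.9% and harm in 0.03% of trials at a 3% rate, and 3.4% and 0.5% at 6%. The total is about 4%, below nominal. At 10% the split is 2.7% and 1.8%, and at 36:36 there is no asymmetry.
- **That chi-square will certainly be run on preeclampsia.** V.A applies it to the outcomes, and preeclampsia is not among them.

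The choice of an exact or corrected test is also routine analysis-plan detail, and that plan is not at hand. The test is therefore a secondary, conditional point.

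**Conclusion.** The point stands as a mismatch between aims, outcomes and size. Aims 2 and 3 promise a determination about preeclampsia that no listed or defined outcome supports. A comparison of 72 women could not settle it at any rate examined: power for a halving is at most 28% (Pearson) or 21% (Fisher), and 80% power would need between 330 and 3,294 women. These figures assume 48:24 arms, a two-sided 0.05 level and no dropout; rates above 6% are assumptions. The mismatch itself rests only on the Protocol's text. It should be corrected, because the plan as written leaves two of its three aims without an answer.

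**What to change.** 1. **Aims 2 and 3 (I.A).** Reword them to estimate, with 95% confidence intervals, the between-arm differences in blood pressure outcomes and preeclampsia in order to inform a definitive trial. State that no conclusion on effectiveness will be drawn.
2. **Outcomes (V.B and synopsis).** List EHR-diagnosed preeclampsia, any and early-onset, counted per woman, as a descriptive outcome with a definition. Name the diagnosis and the gestational age at diagnosis among the abstracted fields in IV.D and Appendix E. EHR abstraction is already planned, but these fields are not explicitly specified.
3. **Analysis (II.C and V.A), secondary.** Give exact confidence intervals for preeclampsia. If it is tested, use an exact test in place of chi-square when an expected count is below 5.
4. **Arm sizes.** Reconcile the 2:1 allocation with the equal groups in the timeline table, since the figures above assume 48:24.

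The cost is wording changes and a small addition to the abstraction form. The downside is a less ambitious stated claim.
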